6.1.2.2. Immune Response to a booster dose

There will be two separate evaluations, performed on evaluable subjects (ATP cohort-booster) following a booster dose:

- Point estimates and 95% CIs for MGIs relative to Day 385 will be computed for vaccine-homologous antibody titers assessed by HI at Day 392 for each vaccine regimen
- Point estimates and 95% CIs for MGIs relative to Day 385 will be computed for vaccine-homologous antibody titers assessed by MN at Day 392 for each vaccine regimen

6.1.2.3. Analysis for immunogenicity (secondary objective)

- Point estimates and 95% CIs for MGIs relative to Day 0 will be computed for vaccine-homologous antibody titers assessed by MN at Day 385 for each vaccine regimen.
- Using vaccine-homologous and vaccine-heterologous antibody titers assessed by HI, the point estimates for SCR, SPR, MGI, and the associated 95% CIs will be computed at 21 days after the second dose.
- Using vaccine-homologous and vaccine-heterologous antibody titers assessed by HI, the point estimates and 95% CIs for GMTs and Seropositivity rates (at all timepoints), and SPRs, SCRs and MGIs at Day 385 will be computed for each vaccine regimen.
- Point estimates and 95% CIs for Seropositivity, GMTs and VRRs for vaccine-homologous/*heterologous* MN titers will be computed for all appropriate timepoints.

All comparisons will be descriptive.

The ATP immunogenicity cohorts (Day 42, persistence or booster) will be used for the related analysis of immunogenicity.

The reverse cumulative distribution curves (RCCs) for HI antibodies against A/Indonesia/05/2005 (H5N1)-like influenza virus at Days 0, 42, 385 and 392 will be performed.

6.1.2.4. Analysis for CMI

- Cell Mediated Immunity (CMI) parameters at Day 0, 42, 385 and 392 will be evaluated in TVC:
 - Antigen-specific CD4+/CD8+ T Cells identified as CD4/CD8+ T- cells producing two or more markers within CD40L, IL-2, TNF- α , IFN- γ upon *in vitro* stimulation using A/Indonesia/05/2005 (H5N1) split virus,
 - The frequency of the response for CD4+/CD8+T-cells stained with probes for various cytokines and activation marker (IFN- γ , TNF- α , IL-2, CD40L) and elicited by vaccine components measured in a sub-cohort of approximately 20 subjects per group at Days 0, 42, 385 and 392 will be described according to the technical specifications provided by R&D (Clinical Data – Information Sheet).

6.1.3. Analysis for safety

- Safety data will be analyzed based on the TVC.
- Analysis will be of subject incidence rates of solicited and unsolicited adverse events (AEs), by solicited local and general AEs terms, and, for unsolicited AEs, by MedDRA preferred term and system organ class. Safety data will be summarized for all subjects by treatment group. The incidence of solicited local and general AEs occurring during 7 days after vaccination will be tabulated with exact 95% CI for each treatment group. The same calculations will be performed for AEs of any

intensity, those with intensity Grade ≥ 2 , and those with intensity of Grade 3, as well as for solicited general events assessed as related to vaccination. All solicited local AEs are considered to be related to vaccination.

- The percentage of subjects with at least one report of an unsolicited AE classified by MedDRA (System Organ Class and Preferred Term) 21 days after each primary vaccination will be tabulated with exact 95% CI for each treatment group. The same tabulation will be performed for Grade 3 unsolicited AEs and for unsolicited AEs that are considered by the investigator to be possibly or probably related to vaccination.
- The percentage of subjects with at least one report of an unsolicited AE classified by MedDRA (System Organ Class and Preferred Term) 30 days after the booster vaccination will be tabulated with exact 95% CI. The same tabulation will be performed for Grade 3 unsolicited AEs and for unsolicited AEs that are considered by the investigator to be possibly or probably related to vaccination.
- The proportion of subjects who begin at least one new concomitant medication during the first 42 days after primary vaccination will be calculated with 95% CI.
- MAEs, AESIs, SAEs, and pIMDs will be summarized through the entire study period. In addition, serious AEs and withdrawals due to AE(s) will be described in detail.

The pIMD listings will include pIMDs reported by the Investigator and those identified from the clinical database search using a list of pre-specified pIMD PTs.

The AESIs listings will include AESIs identified from the clinical database search using a list of pre-specified AESIs PTs and SMQs. The AESIs will include the events listed below and the MedDRA PT or SMQ used to identify reports of these events is provided in parentheses:

- Anaphylaxis (narrow SMQs “Anaphylactic reaction” and “Angioedema”)
- Bell’s palsy (MedDRA PT “VIIth nerve palsy”)
- Convulsion (Narrow SMQ “Convulsions”)
- Demyelination (narrow SMQ “Demyelination”)
- Encephalitis (narrow SMQ “Non-infectious encephalitis”)
- Guillain-Barré syndrome (narrow SMQ “Guillain-Barré syndrome”)
- Neuritis (MedDRA PT “Neuritis”)
- Vasculitis (narrow SMQ “Vasculitis”)

7. STATISTICAL CALCULATIONS

7.1. Derived and transformed data

7.1.1. Demography

For a given subject and a given demographic variable, missing measurement will not be replaced except for incomplete date of birth (DOB) data.

7.1.1.1. Age at vaccination

Age will be calculated as the number of months between the DOB and the date of vaccination.

In some countries, to ensure that the collection of DOB will not jeopardise the privacy of personally identifiable information, only a partial DOB (MMYYYY) will be collected.

Therefore, the 15th of the month will be used to replace the missing date.

In case the day and the months are missing, the date will be replaced by the June 30th of the year.

7.1.2. Immunogenicity

The cut-off value for antibody titer is defined by the laboratory before the analysis. **A seronegative** subject is a subject whose antibody titer is below the cut-off value, and conversely; **a seropositive** subject is one whose antibody titer is greater than or equal to the cut-off value. For this study:

- It is assumed that **HI titers** of < 1:10 will be considered below the cut-off. For the calculations of GMT, HI titers of < 10 will be arbitrarily assigned the value 5.
- It is also assumed that **MN titers** of < 1:28 will be considered below the cut-off. For the calculations of GMT, MN titers of < 28 will be arbitrarily the value 14.

Geometric Mean Titer (GMT) calculations are performed by taking the anti-log of the mean of the log (base 10) transformed inverse titers (the number X would denote the inverse of a titer expressed as “1: X”). Antibody titers below the cut-off of the assay are given an arbitrary value of half the cut-off for the purpose of GMT calculation.

Mean Geometric Increase (MGI) for HI is defined as the geometric mean of the within-subject ratios of the post-vaccination reciprocal HI titer to the **pre-vaccination** HI titer.

Seroconversion Rate (SCR) is defined as the incidence rate of vaccines who have either a pre-vaccination titer recorded as <1:10 for HI and a post-vaccination reciprocal titer \geq 40 or a pre-vaccination reciprocal titer \geq 10 and at least a 4-fold increase in post-vaccination reciprocal titer.

Incidence Rate of HI Reciprocal Titers ≥ 40 (SPR), defined as the percentage of all vaccinees with a serum reciprocal HI antibody titer ≥ 40 post-vaccination, a level of HI antibodies that may correlate with benefit in protection against influenza.

Vaccine Response Rate (VRR) by MN is defined as the post-vaccination reciprocal titer of *vaccines* that have at least 4-fold increase compared with their pre-vaccination reciprocal titer. Antibody titers below the cut-off of the assay are given an arbitrary value of half the cut-off for the purpose of VRR calculation.

Handling of missing immunogenicity data: for a given subject and a given immunogenicity measurement, missing or non-evaluable measurements will not be replaced. Therefore, analyses will exclude subjects with missing or non-evaluable measurements.

7.1.3. Reactogenicity and safety

Incidence rates of AEs will be calculated as the number of subjects who experience the event, divided by the number of subjects in the safety analysis cohort (the TVC).

Handling of missing safety data:

- **Solicited AEs:** For a given subject and the analysis of solicited AEs within 7 days post-vaccination (Days 0 through 6), missing or non-evaluable measurements will not be replaced.
 - The analysis of the solicited AEs will include only vaccinated subjects and doses with documented safety data (i.e., symptom screen/sheet completed, including the response ‘Yes’ or ‘No’ to the solicited symptom page).
 - Subjects who answered “Yes” in the solicited symptom page, but had all symptoms missing are considered as having no solicited symptoms.
 - Subjects who answered ‘Yes’ to the presence of a specific symptom but partially recorded the daily measurement (e.g. intensity missing for Day 3) over the considered solicited period will be included in the summaries and classified according to their maximum observed daily recording over the solicited period.
 - Subjects who answered ‘Yes’ to the presence of a specific symptom but recorded no daily measurement over the considered solicited period will not be counted in the summary of symptoms by grade/category but will be part of the summary corresponding to the ‘All’ category for that symptom.
- **Unsolicited AEs:** For the analysis of unsolicited AEs/MAEs/SAEs/pIMDs/AESIs, all vaccinated subjects will be considered and subjects who did not report an event will be considered as subjects without an event.
- **Concomitant medication and vaccination:** For the analysis of concomitant medications and vaccinations, all vaccinated subjects will be considered and subjects who did not report an event will be considered as subjects without an event.

7.1.3.1. Counting rule

Event	N used for deriving % per subject for vaccination phase
Solicited general symptom	All subjects with at least one solicited general symptom documented as either present or absent (i.e. symptom screen completed)
Solicited local symptom	All subjects with at least one solicited local symptom documented as either present or absent (i.e. symptom screen completed)
Unsolicited symptom MAEs/SAEs/pIMDs/AESIs	All subjects with study vaccine administered
Concomitant medication	All subjects with study vaccine administered
Concomitant vaccination	All subjects with study vaccine administered

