**Table 22 Probability to detect fever during 7-day follow-up after vaccination**

Endpoint	Incidence rate	Num of evaluable subjects	at least X subjects with fever	Prob of detecting at least one subjects with fever*
Fever $\geq 38^{\circ}\text{C}$	22.4%	34	1	$\geq 99.9\%$
Fever $\geq 38.5^{\circ}\text{C}$	10.7%	34	1	97.9%

Assumed a binomial distribution

Based on incidence of fever observed in Q-Pan H5N1-021 in that age group, with 34 evaluable subjects per group the probability of observing at least one subject with fever  $\geq 38^{\circ}\text{C}$  is  $>99.9\%$  assuming a fever incidence rate of 22.4%; and the probability of observing at least one subject with fever  $\geq 38.5^{\circ}\text{C}$  is 97.9% assuming the incidence rate of 10.7%.

**Table 23 Power to meet LL of 95% CI for SCR>40% and LL of 95%CI for SPR>70% in one of the vaccine group (without Type I error adjustment)**

Endpoint	Success Criteria	N evaluable in each group	Reference value 	Power 
HI response: SCR	LL of 95% CI > 40%	34	90%	>99.99%
HI response: SPR	LL of 95% CI > 70%	34	90%	75.04%

Key: LL=Lower Limit; SP=Seroprotection (HI antibody titers > 1:40); SPR=Seroprotection rate; CI=confidence interval.

Source of reference values: lower 95% confidence bound of SPR at Day 42 for Q-Pan-021 in children 6-35 months of age receiving 1.9 µg H5N1 HA antigen adjuvanted with AS03B.

PASS 2005 [Miettinen, 1985], 2-sided one proportion test, alpha=5%.

As one of the secondary objectives, HI responses in each vaccine regimen 21 days post dose 2 will be evaluated. The power to meet LL of 95% CI for SCR>40% and LL of 95%CI for SPR>70% is 75.0% in one vaccine group (no type I error adjustment).

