2.2. Study groups

Approximately 37 subjects are planned to be enrolled in each of the 5 following study groups:

Study groups	Number of subjects	Epochs	
		Epoch 001 (Primary Series)	Epoch 002 (Booster)
190_B	37	●	●
090_C	37	●	●
190_C	37	●	●
375_C	37	●	●
375_D	37	●	●

Treatment name	Vaccine/Product name (Formulation)	Study Groups				
		190_B	090_C	190_C	375_C	375_D
1.9 mcg H5N1 HA + AS03B	FLU-Q-PAN (A/Indonesia/05/2005 H5N1 HA, 15 µg/mL)	●				
	AS03A (AS03 47.44 mg/mL, final vaccine dose contains 5.93 mg tocopherol)	●				
0.9 mcg H5N1 HA + AS03C	FLU-Q-PAN (A/Indonesia/05/2005 H5N1 HA, 15 µg/mL)		●			
	AS03A (AS03 47.44 mg/mL, final vaccine dose contains 2.97 mg tocopherol)		●			
1.9 mcg H5N1 HA + AS03C	FLU-Q-PAN (A/Indonesia/05/2005 H5N1 HA, 15 µg/mL)			●		
	AS03B (AS03 23.72 mg/mL; final vaccine dose contains 2.97 mg tocopherol)			●		
3.75 mcg H5N1 HA + AS03C	FLU-Q-PAN (A/Indonesia/05/2005 H5N1 HA, 30 µg/mL)				●	
	AS03B (AS03 23.72 mg/mL; final vaccine dose contains 2.97 mg tocopherol)				●	
3.75 mcg H5N1 HA + AS03D	FLU-Q-PAN (A/Indonesia/05/2005 H5N1 HA, 30 µg/mL)					●
	AS03C (AS03 11.86 mg/mL; final vaccine dose contains 1.48 mg tocopherol)					●
3.75 mcg H5N1 HA *	FLU-Q-PAN (A/Indonesia/05/2005 H5N1 HA, 15 µg/mL)	●	●	●	●	●

*Booster vaccination to subjects in all study groups

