5.2. Cohort for analysis of the immunogenicity-fever score

The analysis cohort for combined immunogenicity and safety of the two-dose primary series will include all subjects in the ATP cohort for immunogenicity analysis at Day 42 for whom temperature measurements are available during the first 3 days after both vaccine doses 1 and 2.

Subjects without immunogenicity results at Day 42 or for whom one or more daily temperature measurements are missing during the first 3 days after either vaccine dose [dose 1 or dose 2] will be excluded from the immunogenicity/fever index calculation for the primary series.

The list of applicable elimination codes for each cohort can be found in the study specific form FORM-9000036402-13 Criteria for eliminating subjects from the analyses and filled in CARS.

Cohort	Elimination codes	Eli Type
ATP cohort for Day 42 analysis of the immunogenicity	1030;1040;1050;1060;1070;1080; 1090; 2010; 2040; 2050; 2060; 2070; 2080; 2090; 2100; 2500.	PR
ATP - Day 385 (Persistence)	1030;1040;1050;1060;1070;1080 ; 1090; 2010; 2040; 2050; 2060; 2070; 2080; 2090; 2100; 2500.	PE
ATP Day 392 post-booster dose.	1030;1040;1050;1060;1070;1080; 1090; 2010; 2040; 2050; 2060; 2070; 2080; 2090; 2100; 2500.	MA (including PR)

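### The shared denominator for solicited general symptoms counts a child with no temperature and no fever answer as a non-event in the 7-day fever tables

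*SAP*

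**What the plan says.** SAP Section 7.1.3.1 (Counting rule) gives a single N for the percentage of children with a solicited general symptom: "All subjects with at least one solicited general symptom documented as either present or absent (i.e. symptom screen completed". Protocol Table 15 lists four such symptoms: drowsiness, fever, irritability/fussiness and loss of appetite. Documentation of any one of them brings the child into N for all four.

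SAP Section 7.1.3 adds the missing-data rules for solicited events:

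- In general, "missing or non-evaluable measurements will not be replaced", and the analysis is limited to children and doses with a completed symptom sheet, including a Yes or No answer to the symptom page.
- Children who answered Yes on the page "but had all symptoms missing are considered as having no solicited symptoms".
- Children who marked a specific symptom Yes but "recorded no daily measurement over the considered solicited period will not be counted in the summary of symptoms by grade/category"; they stay in the all-grades row for that symptom.
- The opening sentence of the section says that adverse event incidence is the number with the event "divided by the number of subjects in the safety analysis cohort (the TVC". That is a wider denominator than the one in Section 7.1.3.1.

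No rule removes a child from the fever row when fever itself is undocumented.

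The co-primary fever index is handled separately. SAP Section 5.2 and Protocol Section 10.4.3 exclude children "for whom one or more daily temperature measurements are missing during the first 3 days after either vaccine dose".

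**The concern.** Fever differs from the other general symptoms because it is defined by a thermometer reading. The other three are graded by observation (Protocol Table 18). A card with those rows filled in and the temperature row blank is therefore possible. For such a child, unless fever was marked Yes, the shared N has the same effect on the fever percentage as recording no fever, and the SAP does not say so. For unsolicited events, by contrast, Section 7.1.3 states openly that a child who reported no event is taken as having none.

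The grade rows have a related gap. A child with fever marked Yes and no reading is left out of every grade row but stays in N, so the percentages by temperature grade are diluted.

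At stake are the descriptive 7-day fever percentages and their exact confidence intervals. SAP Section 7.4 names fever as the key indicator of reactogenicity for dose selection and proposes no selection algorithm, so these percentages may be weighed alongside the index. If missing temperatures were unevenly spread over the five groups, part of an apparent difference between regimens could come from the denominator.

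**Working it through.** **Inputs**

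- Planned group size: 37 (SAP Section 2.2: "Approximately 37 subjects are planned to be enrolled in each of the 5 following study groups").
- Assumed incidence of fever at or above 38.0°C: 22.4%; at or above 38.5°C: 10.7% (Protocol Table 22).
- m = children in a group who are in N with no temperature on Days 0-6 and fever not marked Yes. The documents give no value; 1 to 5 of 37 is an assumed range.

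**Step 1: reproduce the protocol's figures.** Table 22 states that "with 34 evaluable subjects per group the probability of observing at least one subject with fever" exceeds 99.9% at the lower threshold and is 97.9% at the higher one.

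- 1 − (1 − 0.224)^34 = 99.98%
- 1 − (1 − 0.107)^34 = 97.87%

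Both agree. This confirms the incidence inputs; it does not test the counting rule.

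**Step 2: expected effect of the shared N.** Suppose the true incidence is p in all children and missing readings are unrelated to fever. Then the expected reported rate is p × (37 − m)/37, and the loss is p × m/37.

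| m | p = 22.4% | Loss (points) | p = 10.7% | Loss (points) |
|---|---|---|---|---|
| 0 | 22.4% | 0 | 10.7% | 0 |
| 1 | 21.8% | 0.6 | 10.4% | 0.3 |
| 2 | 21.2% | 1.2 | 10.1% | 0.6 |
| 3 | 20.6% | 1.8 | 9.8% | 0.9 |
| 5 | 19.4% | 3.0 | 9.3% | 1.4 |

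With N = 37 − m, the expected rate under this assumption stays at p.

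**Step 3: the same in counts.** Take 8 children with observed fever in a group of 37. The shared N always gives 8/37 = 21.6%. A fever-specific N gives 8/36 = 22.2% (m = 1), 8/34 = 23.5% (m = 3) or 8/32 = 25.0% (m = 5).

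**Step 4: what the data can and cannot say.** With m = 3, the true proportion lies between 8/37 = 21.6% (none of the three febrile) and 11/37 = 29.7% (all three febrile). The shared N reports the bottom of that range. The fever-specific 23.5% lies inside it.

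**Step 5: grade rows.** Suppose one child in 37 has fever marked Yes and no reading, and has the same chance of reaching 38.5°C as other febrile children: 10.7/22.4 = 0.478. The expected loss in the percentage at or above 38.5°C is 0.478/37 = 1.3 points for that child.

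**Step 6: scale.** One child in 37 is 2.7 points. The exact 95% interval for 8/37 is 9.8% to 38.2%. A difference in m between groups of 0 against 3 would produce an expected difference of 1.8 points at 22.4%.

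**The case against.** Most of the case against stands, and it limits the point.

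- **A reader might infer that every child without a reading is counted as afebrile.** The SAP does not support that. Fever marked Yes without a reading is kept in the all-grades row. A page answered No plausibly documents fever as absent. What is left is a page answered Yes, another general symptom filled in, fever not marked Yes, and no temperature on any of seven days.
- **Conduct should keep that set small.** Temperature is to be recorded each evening (Protocol Table 15 note), the sponsor supplies a thermometer (Protocol Section 5.6.6), and diary cards are verified and chased (Protocol Section 5.6.12).
- **A reader might see a contradiction with SAP Section 5.2.** There is none. The fever index sums six daily readings and needs all six; the 7-day incidence uses the maximum observed value, so partial data suffice. Different endpoints may have different missing-data rules.
- **A reader might also see a breach of the rule against replacing missing values.** No value is imputed. The SAP applies a sheet-level definition of documented data and leaves its effect on the fever row unstated.
- **The direction of error is not assured.** If parents skipped the thermometer because the child looked well, the shared N is nearer the truth and a fever-specific N would overstate fever.
- **The effect is small against sampling error**, as the interval in the working shows.

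The textual gap itself is not answered. For the residual children, nothing in Sections 7.1.3 or 7.1.3.1 takes them out of the fever row, and no count of them is planned, so a reader of the tables could not tell which scenario applies.

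**Conclusion.** The point holds in a limited form. As written, the counting rule includes children whose fever status is undocumented in the 7-day fever denominator as non-events, and it dilutes the grade rows when fever is marked Yes without a reading. It can only lower the reported percentage or leave it unchanged relative to a fever-specific N.

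The size is about 0.6 points per such child in a group of 37 at 22.4%, and about 0.3 points at 10.7%. This assumes that missing readings are unrelated to fever. The number of such children is not in the documents, and if there are none the effect is zero. Understatement of the true rate requires both that such children exist and that some of them were febrile, so the documents do not show that fever will be understated.

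The co-primary immunogenicity-fever index is unaffected because its cohort is defined separately. The matter concerns secondary, descriptive tables. It is still worth correcting because the rule always returns the lowest rate compatible with the data, on the symptom that the plan treats as its key indicator of reactogenicity, and because Sections 7.1.3 and 7.1.3.1 give different denominators.

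**What to change.** In SAP Section 7.1.3.1, define N separately for each solicited symptom as the children (and doses) for whom that symptom was documented as present or absent. For fever, this means at least one temperature on Days 0-6 after the dose, or fever marked present, or the symptom page answered No.

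Report, per group and dose, the number of children with no temperature reading, split into fever marked present and fever not documented. The first count shows how far the grade rows are diluted; the second lets a reader judge either missing-data scenario.

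Reconcile this N with the TVC denominator in the opening sentence of Section 7.1.3. State whether children with a Yes page and every symptom blank belong in the symptom-specific N.

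The cost is a short SAP edit and a small programming change. The downside is that N will differ slightly between symptoms in the same table.
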